Appendix 3 Schedule of Pharmacokinetic and Immunogenicity Sampling

Table 1Maintenance Phase of Dose-Escalation Arms A & B and Maintenance Phase of Dose-Expansion
Cohort

Study Visit (Maintenance Phase)	Venetoclax PK (Plasma Sample)	Atezolizumab PK (Serum Sample)	Atezolizumab ADA (Serum Sample)
Cycle 1, Day 1		Pre-infusion of atezolizumab	Pre-infusion of atezolizumab
Cycle 2, Day 1	Predose (Within 1 hour before dosing) 4 hours postdose (± 20 minutes)	Pre-infusion of atezolizumab (Within 24 hours prior to dosing)	Pre-infusion of atezolizumab (Within 24 hours prior to dosing)
Cycle 3, Day 1		Pre-infusion of atezolizumab (Within 24 hours prior to dosing)	Pre-infusion of atezolizumab (Within 24 hours prior to dosing)
Cycle 4, Day 1	Predose (Within 1 hour before dosing) 4 hours postdose (± 20 minutes)	Pre-infusion of atezolizumab (Within 24 hours prior to dosing) 30 minutes after end of atezolizumab infusion (± 10 minutes)	Pre-infusion of atezolizumab (Within 24 hours prior to dosing)
Cycle 8, Day 1		Pre-infusion of atezolizumab (Within 24 hours prior to dosing)	Pre-infusion of atezolizumab (Within 24 hours prior to dosing)
Cycle 12, Day 1		Pre-infusion of atezolizumab (Within 24 hours prior to dosing)	Pre-infusion of atezolizumab (Within 24 hours prior to dosing)
Cycle 16, Day 1		Pre-infusion of atezolizumab (Within 24 hours prior to dosing)	Pre-infusion of atezolizumab (Within 24 hours prior to dosing)
At Treatment Discontinuation ^a		Anytime during visit	Anytime during visit

ADA = anti-drug antibody; PK = pharmacokinetic.

Notes:

PK and ADA samples are to be collected, prepared, and shipped according to procedures outlined in the separate laboratory manual.

Record exact date and time of venetoclax dosing on the day of and the day prior to the date of PK sampling. Patients should record doses taken at home in a dosing diary.

Record the date and time of administration of atezolizumab on the day of PK sampling.

Record exact date and time of all PK sample collections.

Sample collection times are relative to the administration of the study drug being measured.

^a Only one sample will be taken at Treatment Discontinuation. Patients may need to discontinue treatment in either the induction or the maintenance phase. Therefore, this sample appears in both Table 1 and Table 2 of Appendix 3.

Table 2	Induction Phase of	Dose-Escalation	Arm B and	Induction	Phase of	Dose-Expansion	Cohort
---------	--------------------	-----------------	-----------	-----------	----------	----------------	--------

Study Visit (Induction Phase)	Venetoclax PK (Plasma Sample) ^a	Atezolizumab PK (Serum Sample)	Atezolizumab ADA (Serum Sample)	Carboplatin PK (Plasma Sample) ^b	Etoposide PK (Plasma Sample) ^b
Cycle 1, Day 1	6 hours postdose (± 20 minutes)	Pre-infusion of atezolizumab (Within 24 hours prior to dosing) 30 minutes after end of atezolizumab infusion	Pre-infusion of atezolizumab (Within 24 hours prior to dosing)	Pre-infusion (within 1 hour before dosing) 5–10 min prior to end of infusion 1 hours after end of infusion (± 10 minutes) 3 hours after end of infusion (± 10 minutes) 5 hours after end of infusion (± 10 minutes)	Pre-infusion (within 1 hour before dosing) 5–10 min prior to end of infusion 1 hours after end of infusion (± 10 minutes) 3 hours after end of infusion (± 10 minutes) 5 hours after end of infusion (± 10 minutes)
Cycle 1 Day 2	Predose (within 1 hour before dosing)			24 hours after end of prior day infusion (± 2 hours)	24 hours after end of prior day infusion and prior to dosing on C1D2 (± 2 hours)
Cycle 1 Day 3 (Day 4 or Day 5 are also acceptable to avoid weekend/ holidays)	Predose (within 1 hour before dosing) 4 hours postdose (± 20 minutes)				
Cycle 1 Day 8	Predose (within 1 hour before dosing)				
Cycle 2, Day 1		Pre-infusion of atezolizumab (Within 24 hours prior to dosing)	Pre-infusion of atezolizumab (Within 24 hours prior to dosing)		

Table 2	Induction Phase o	f Dose-Escalation A	rm B and Induction	Phase of Dose-Ex	pansion Cohort (cont.)
---------	-------------------	---------------------	--------------------	------------------	------------------------

Study Visit (Induction Phase)	Venetoclax PK (Plasma Sample) ª	Atezolizumab PK (Serum Sample)	Atezolizumab ADA (Serum Sample)	Carboplatin PK (Plasma Sample) ^b	Etoposide PK (Plasma Sample) ^b
Cycle 4, Day 1		Pre-infusion of atezolizumab (Within 24 hours prior to dosing) 30 minutes after end of atezolizumab infusion (± 10 minutes)	Pre-infusion of atezolizumab (Within 24 hours prior to dosing)		
At Treatment Discontinuation ^c		Anytime during visit	Anytime during visit		

ADA = anti-drug antibody; PK = pharmacokinetic; RP2D = recommended Phase II dose.

Notes:

PK and ADA samples are to be collected, prepared and shipped according to procedures outlined in the separate laboratory manual.

Record exact date and time of venetoclax dosing on the day of and the day prior to the date of PK sampling. Patients should record doses taken at home in a dosing diary.

Record the date and time of administration of atezolizumab, carboplatin, and etoposide on the day of PK sampling.

Record exact date and time of all PK sample collections

Sample collection times are relative to the administration of the study drug being measured.

^a If subject will receive venetoclax in the maintenance phase only, then venetoclax PK samples will not be taken in the induction phase.

^b Carboplatin and etoposide PK sampling will only be done for patients enrolling into the expansion phase (i.e., after dose-escalation is complete and a RP2D for venetoclax has been determined).

^c Only one sample will be taken at Treatment Discontinuation. Patients may need to discontinue treatment in either the induction or the maintenance phase. Therefore, this sample appears in both Table 1 and Table 2 of Appendix 3.

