3.1.2.1 Maintenance Only (Arm A)

In the maintenance-only arm, venetoclax will be explored on a continuous dosing schedule at doses ranging from 400 mg QD to 800 mg/QD in the following dose-escalation treatment cohorts using a standard 3+3 design:

• Maintenance Cohort A1 (Dose Level 1):

Venetoclax: 400 mg QD continuous on Days 1–21 Atezolizumab: 1200 mg every 3 weeks (Q3W) on Day 1

• Maintenance Cohort A2 (Dose Level 2):

Venetoclax: 800 mg QD continuous on Days 1–21 Atezolizumab: 1200 mg Q3W on Day 1

Dose de-escalation to 200 mg QD continuous on Days 1–21 may be explored if DLTs are experienced and adverse events are thought to be potentially mitigated with a lower dose of venetoclax (refer to Figure 3).

Once tolerability and dose are established in the maintenance-only arm (Arm A), the induction followed by maintenance arm (Arm B) will be opened, based on thorough review led by the Medical Monitor in consultation with the Principal Investigators and a committee composed of, at a minimum, the following Sponsor representatives: statistician, safety scientist, PK scientist, and clinical scientist. Patients on maintenance therapy who do not experience unacceptable toxicity and have evidence of clinical benefit (as defined in the protocol) may continue to receive maintenance study treatment every 21 days until documented disease progression determined by investigator or unacceptable toxicity, whichever occurs first.

DLT = dose-limiting toxicity; ECOG = Eastern Cooperative Oncology Group; ES = extensive-stage; I = induction; M = maintenance; MTD = maximum tolerated dose; RP2D-M = recommended Phase II dose for maintenance; SCLC = small cell lung cancer.

3.1.2.2 Induction Plus Maintenance (Arm B):

In the induction plus maintenance arm (Arm B; see Figure 4), venetoclax will be explored on a non-continuous (NC) dosing schedule in the following dose-escalation treatment cohorts using a standard 3+3 design:

- Induction Cohort B1 (Dose Level 1): Venetoclax: 200 mg/QD NC on Days 1–7 Atezolizumab: 1200 mg Q3W on Day 1 Carboplatin: AUC 5 mg/mL min (Calvert formula) on Day 1 Etoposide: 100 mg/m² on Days 1–3
- Induction Cohort B2 (Dose Level 2): Venetoclax: 400 mg/QD NC on Days 1–7 Atezolizumab: 1200 mg Q3W on Day 1 Carboplatin: AUC 5 mg/mL min (Calvert formula) on Day 1 Etoposide: 100 mg/m² on Days 1–3

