- Induction Cohort B3 (Dose Level 3): Venetoclax: 800 mg/QD NC on Days 1–7 Atezolizumab: 1200 mg Q3W on Day 1 Carboplatin: AUC 5 mg/mL min (Calvert formula) on Day 1 Etoposide: 100 mg/m² on Days 1–3
- Induction Cohort B4 (Dose Level 4): Venetoclax: 800 mg/QD NC on Days 1–14 Atezolizumab: 1200 mg Q3W on Day 1 Carboplatin: AUC 5 mg/mL min (Calvert formula) on Day 1 Etoposide: 100 mg/m² on Days 1–3

Figure 4 Study Schema: Dose-Escalation, Induction (Arm B)

Note: Cohorts may incorporate primary prophylactic growth factor support as described below and in Section 3.1.4.

DLT = dose-limiting toxicity; MTD = maximum tolerated dose; NC = non-continuous; RP2D-I = recommended Phase II dose for induction.

Patients may be treated in up to five NC dosing cohorts (i.e., venetoclax 200 mg Days 1–7 NC, 400 mg Days 1–7 NC, 800 mg Days 1–7 NC, 800 mg Days 1–14 NC, and any of the dose levels integrating primary prophylactic growth factor support). Specifically, at the initiation of the induction phase of dose–escalation Arm B, cohorts will be treated without primary prophylactic growth-colony stimulating factor (G-CSF). If 2 or more patients out of the first 6 DLT-evaluable patients in a particular cohort without primary prophylactic growth factor support experienced neutropenia-related adverse events (Grade 4 neutropenia resulting in treatment delay beyond 14 days or Grade 3–4 febrile neutropenia), then that particular cohort level will be tested again at the same dose *level* with mandatory primary prophylactic growth factor support (see Section 3.1.4 for additional details). Of note, primary G-CSF prophylaxis is only mandated during induction and not during maintenance therapy. Such cohorts will be designated with "-P" to denote the primary G-CSF prophylactic requirement (e.g., Cohort B1-P). Subsequent dose–escalation cohorts will then be required to incorporate primary G-CSF prophylaxis.

Patients will be treated for a total of 4 cycles of study treatment for induction. Each cycle will consist of 21 days. Dose-escalation will continue until DLTs are observed. If there is excessive toxicity and DLTs at the lowest tested venetoclax dose in induction, then venetoclax will be subsequently expanded in the maintenance setting only.

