- ^{cc} On Day 1 of each cycle, patients will receive treatment in the following order: 1) atezolizumab, 2) carboplatin, 3) etoposide, and 4) venetoclax. On Days 2 and 3, patients will receive etoposide infusions. Refer to Section 4.3.2 for specific details. Venetoclax is administered QD for 7 or 14 days as described in Section 3.1.2.

Atezolizumab—F. Hoffmann-La Roche Ltd

Page 167 of 214 Protocol GO41864, Version 2

^s During the maintenance phase, PCI is permitted as per local standard of care and will be reported on the Prophylactic Cranial Irradiation eCRF.

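### Appendix 3 times the Cycle 1 Day 8 venetoclax sample against a dose that the 7-day induction cohorts do not take

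*Combined protocol and SAP*

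**What the plan says.** Appendix 3 Table 2 covers induction in both the escalation and the expansion phase. Its Cycle 1 Day 8 row has a single venetoclax instruction, "Predose (within 1 hour before dosing", with no variant by cohort. The notes to the table define sample times by reference to dosing of the drug being assayed.

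Section 3.1.2.2 gives the dosing days:

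- B1: "Venetoclax: 200 mg/QD NC on Days 1–7"
- B2: "Venetoclax: 400 mg/QD NC on Days 1–7"
- B3: "Venetoclax: 800 mg/QD NC on Days 1–7"
- B4: "Venetoclax: 800 mg/QD NC on Days 1–14"

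Footnote cc of Appendix 2 confirms both durations: "Venetoclax is administered QD for 7 or 14 days as described in Section 3.1.2". Section 3.1.2.2 also says "Patients may be treated in up to five NC dosing cohorts", the fifth being a repeat of a level with growth-factor prophylaxis.

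The Day 8 column of Appendix 2 carries a ±1-day window. Footnote c drops most Day 8 assessments in expansion but keeps PK sampling. On dose times, the Appendix 3 note reads "Record exact date and time of venetoclax dosing on the day of and the day prior to the date of PK sampling"; exact sample times are also required. Section 4.3.2.2 gives patients a diary for dose dates and times and asks for dosing at about the same time each morning. Section 6.6 commits to tabulating and summarizing concentrations in suitable groups, without defining them.

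**The concern.** A predose sample needs a dose. In B1 to B3 there is none on Day 8, so a site cannot comply and must choose its own draw time. The other controls do not help. Section 4.3.2.2 fixes timing on PK days by having the dose taken in clinic, which has no effect when no dose is due. The biomarker blood due on the same day (Appendix 4) may be taken at any point in the visit, so nothing points to a morning draw.

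This is the last venetoclax sample of induction: Table 2 lists none in Cycles 2 to 4. It is therefore the only level after a full week of dosing with chemotherapy. Characterizing venetoclax in that combination is a stated PK objective (Sections 2.1.2 and 2.2.3), and Section 3.1.4 has PK data, if available, reviewed before the induction RP2D is chosen. Apart from the normal one-hour predose allowance, the timing error runs one way: a draw that misses the 24 h point is late and reads low.

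**Working it through.** The plan states no figure for this point, so there is none to reproduce. The check sets dosing days against the sampling day, then converts the possible delay into concentration.

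**Step 1. Is there a Day 8 dose?** From Section 3.1.2.2, the last dosing day is 7 in B1, B2 and B3 and 14 in B4. Three of four named levels have no Day 8 dose. An expansion on a 7-day induction schedule would add up to 20 patients (Section 6.1).

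**Step 2. Hours since last dose.** Assumptions, not in the documents: daily dose at 08:00; where no dose is due, the draw falls between 07:00 and 17:00.

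| Draw day | 7-day cohorts | B4 |
|---|---|---|
| Day 7, before the dose | 23–24 h | 23–24 h |
| Day 8 | 23–33 h | 23–24 h |
| Day 9 | 47–57 h | 23–24 h |

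Days 7 and 9 arise only if the ±1-day visit window applies to the PK draw.

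**Step 3. Level relative to the 24 h value.** Assume mono-exponential decline with half-life T of 12 to 36 h, which is again an assumption. At t hours after the dose, ratio = 0.5^((t − 24)/T).

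| Time since dose | T = 12 h | T = 36 h |
|---|---|---|
| 24 h | 1.00 | 1.00 |
| 33 h | 0.5^(9/12) = 0.59 | 0.5^(9/36) = 0.84 |
| 48 h | 0.5^(24/12) = 0.25 | 0.5^(24/36) = 0.63 |
| 57 h | 0.5^(33/12) = 0.15 | 0.5^(33/36) = 0.53 |

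**Step 4. Is the last dose time captured?** For a Day 8 draw, the two days named in the note are Days 8 and 7, so the Day 7 dose is recorded. For a Day 9 draw they are Days 9 and 8. A 7-day patient took nothing on either, so the last dose time is only in the patient diary.

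**Step 5. Effect of an anchored draw.** At 24 h ± 2 h after the Day 7 dose, the ratio stays between 0.5^(2/12) = 0.89 and 2^(2/12) = 1.12 for T = 12 h, and between 0.96 and 1.04 for T = 36 h.

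**The case against.** The best defence is that ordinary practice will usually give the right sample. Patients dose in the morning, so a morning visit on Day 8 is about 24 h after the Day 7 dose, the same point in the interval as B4's trough. A reader might infer that the 7-day cohorts yield a washout level in general. The documents do not support that: it happens only with a late Day 8 draw or a Day 9 draw.

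The Day 9 case is itself open. Table 2 names acceptable alternative days in its Cycle 1 Day 3 row and none for Day 8, which suggests the visit window may not carry over to PK. Against that, Section 4.5 and the Appendix 2 header allow assessments within stated windows, and nothing exempts this draw.

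A reader might also infer that late 7-day values will be tabulated with B4 troughs. Section 6.6 does not say so. It leaves the grouping open and permits population PK, which can use actual times. That analysis is optional, however, while the summary tables are committed.

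Nor is the comparison of 200, 400 and 800 mg biased by schedule. B1, B2 and B3 share one schedule and one ambiguity, so loose timing adds noise to it. B3 and B4 have identical planned dosing through Day 7, so their Day 8 contrast tests no planned exposure difference; the risk there is that late draws make B3 look lower than it is.

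The Day 3 samples (Day 4 or 5 also allowed) are timed during dosing in every cohort. Under the same half-lives, a Day 3 predose level after two doses is 1 − 0.5^(48/T) of steady state: 0.94 at T = 12 h and 0.60 at T = 36 h. After seven doses, the Day 8 level is 1 − 0.5^(168/T): 1.00 and 0.96. Day 3 therefore replaces Day 8 only if the half-life is short.

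Section 4.5.7 allows alternative PK assessments where Appendix 3 times prove difficult to obtain. That permits a repair but does not make one. What stands of the objection limits the size of the problem; the row still cannot be followed as written.

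**Conclusion.** The sampling row and the dosing schedules contradict each other in B1, B2 and B3, and would do so in any growth-factor repeat of those levels or any expansion on a 7-day schedule. The time since last dose is then not controlled by the protocol. For a draw at the usual hour on Day 8 the loss is nil. For a draw 9 h later the level would be 0.59 to 0.84 of the 24 h value, and at 48 h 0.25 to 0.63. Those ranges rest on the assumed 12 to 36 h half-life and mono-exponential decline, and the 48 h case also needs the ±1-day window to apply. A reader might take an understatement of 37 to 75% (1 − 0.63 to 1 − 0.25) as the expected error. It is the Day 9 extreme, and nothing in the documents says how often it would occur.

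The consequence is confined to the PK data and their summary. No DLT rule and no ORR analysis uses this sample. The repair is worth making because it is specific and nearly free.

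**What to change.** Reconcile the Day 8 row of Appendix 3 Table 2 with the dosing schedules by splitting it. For 14-day schedules keep the Day 8 predose draw. For 7-day schedules, time the draw from the Day 7 dose, for example 24 h ± 2 h after it, and state that the ±1-day visit window does not apply to this draw.

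Reword the dose-time note so that the date and time of the last venetoclax dose before each PK sample are recorded. In Section 6.6, either summarize by actual time since last dose or keep the 7-day and 14-day schedules apart.

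The cost is the ±1-day flexibility for one draw in the 7-day cohorts. No dose changes, and no visit or sample is added.

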Appendix 4 Schedule of Biomarker Assessments

Table 1 Blood Samples for Biomarker Analysis

Treatment Period	Visit	Timepoint	Sample Type
Induction and Maintenance	Cycle 1, Day 1	Pre-infusion	Blood for plasma and serum Whole blood sample
			Whole blood RBR sample for genetic research (for consented patients)
Induction	Cycle 1, Day 2	Pre-infusion	Whole blood sample
	Cycle 1, Day 8	At anytime during the visit	Whole blood sample
	Cycle 1, Day 15	At anytime during the visit	Blood for plasma and serum Whole blood sample
	Cycle 2-4, Day 1	Pre-infusion	Blood for plasma and serum Whole blood sample
Maintenance	Cycle 1- 4, Day 1 (and every subsequent odd cycle), Day 1	Pre-infusion	Blood for plasma and serum
	Every Cycle , Day 1	Pre-infusion	Whole blood sample
Induction and Maintenance	Study Treatment/Early Discontinuation Visit	At any time during the visit	Blood for plasma and serum Whole blood sample

Visit	Timepoint	Requirement	Sample Type
Screening	Pre-infusion	Mandatory	FFPE block or partial block preferred or up to 15 freshly serial cut, unstained slides
Anytime During Study Treatment or During Survival follow-up phase	Pre-infusion	Optional	 Fresh Core Biopsy (3 cores) FFPE block or partial block preferred or up to 15 freshly serial cut, unstained slides
Study Treatment/Early Discontinuation Visit	At time of study treatment/ early discontinuation visit (if the reason for discontinuation was PD) ^a	Mandatory (if deemed clinically feasible)	 Fresh Core Biopsy (3 cores) at site of progression if accessible or from any other lesion FFPE block or partial block preferred or up to 15 freshly serial cut, unstained slides

Table 2 Tissue Sample for Biomarker Analysis

^a Must be taken before next line of therapy begins. In case new line therapy is purely antihormonal, biopsy could be taken after it is started.

Appendix 5 Response Evaluation Criteria in Solid Tumors, Version 1.1 (RECIST v1.1)

Selected sections from the Response Evaluation Criteria in Solid Tumors, Version 1.1 (RECIST v1.1), (Eisenhauer et al. 2009) are presented below, with slight modifications from the original publication and the addition of explanatory text as needed for clarity.¹

TUMOR MEASURABILITY

At baseline, tumor lesions/lymph nodes will be categorized as measurable or non-measurable as described below. All measurable and non-measurable lesions should be assessed at screening and at subsequent protocol-specified tumor assessment timepoints. Additional assessments may be performed as clinically indicated for suspicion of progression.

DEFINITION OF MEASURABLE LESIONS

Tumor Lesions

Tumor lesions must be accurately measured in at least one dimension (longest diameter in the plane of measurement is to be recorded) with a minimum size as follows:

- 10 mm by computed tomography (CT) or magnetic resonance imaging (MRI) scan (CT/MRI scan slice thickness/interval ≤5 mm)
- 10-mm caliper measurement by clinical examination (lesions that cannot be accurately measured with calipers should be recorded as non-measurable)
- 20 mm by chest X-ray

Malignant Lymph Nodes

To be considered pathologically enlarged and measurable, a lymph node must be \geq 15 mm in the short axis when assessed by CT scan (CT scan slice thickness recommended to be \leq 5 mm). At baseline and follow-up, only the short axis will be measured and followed. Additional information on lymph node measurement is provided below (see "Identification of Target and Non-Target Lesions" and "Calculation of Sum of Diameters").

¹ For clarity and for consistency within this document, the section numbers and cross-references to other sections within the article have been deleted and minor changes have been made.

DEFINITION OF NON-MEASURABLE LESIONS

Non-measurable tumor lesions encompass small lesions (longest diameter < 10 mm or pathological lymph nodes with short axis \geq 10 mm but < 15 mm) as well as truly non-measurable lesions. Lesions considered truly non-measurable include leptomeningeal disease, ascites, pleural or pericardial effusion, inflammatory breast disease, lymphangitic involvement of skin or lung, peritoneal spread, and abdominal mass/abdominal organomegaly identified by physical examination that is not measurable by reproducible imaging techniques.

SPECIAL CONSIDERATIONS REGARDING LESION MEASURABILITY

Bone lesions, cystic lesions, and lesions previously treated with local therapy require particular comment, as outlined below.

Bone Lesions:

- Technetium-99m bone scans, sodium fluoride positron emission tomography scans, and plain films are not considered adequate imaging techniques for measuring bone lesions. However, these techniques can be used to confirm the presence or disappearance of bone lesions.
- Lytic bone lesions or mixed lytic-blastic lesions with identifiable soft tissue components that can be evaluated by cross-sectional imaging techniques such as CT or MRI can be considered measurable lesions if the soft tissue component meets the definition of measurability described above.
- Blastic bone lesions are non-measurable.

Cystic Lesions:

- Lesions that meet the criteria for radiographically defined simple cysts should not be considered malignant lesions (neither measurable nor non-measurable) since they are, by definition, simple cysts.
- Cystic lesions thought to represent cystic metastases can be considered measurable lesions if they meet the definition of measurability described above. However, if non-cystic lesions are present in the same patient, these are preferred for selection as target lesions.

Lesions with Prior Local Treatment:

• Tumor lesions situated in a previously irradiated area or in an area subjected to other loco-regional therapy are usually not considered measurable unless there has been demonstrated progression in the lesion.

METHODS FOR ASSESSING LESIONS

All measurements should be recorded in metric notation, using calipers if clinically assessed. All baseline evaluations should be performed as close as possible to the treatment start and never more than 4 weeks before the beginning of the treatment.

The same method of assessment and the same technique should be used to characterize each identified and reported lesion at baseline and during the study. Imaging-based evaluation should always be the preferred option.

CLINICAL LESIONS

Clinical lesions will only be considered measurable when they are superficial and \geq 10 mm in diameter as assessed using calipers (e.g., skin nodules). For the case of skin lesions, documentation by color photography, including a ruler to estimate the size of the lesion, is suggested.

CHEST X-RAY

Chest CT is preferred over chest X-ray, particularly when progression is an important endpoint, since CT is more sensitive than X-ray, particularly in identifying new lesions. However, lesions on chest X-ray may be considered measurable if they are clearly defined and surrounded by aerated lung.

CT AND MRI SCANS

CT is the best currently available and reproducible method to measure lesions selected for response assessment. In this guideline, the definition of measurability of lesions on CT scan is based on the assumption that CT slice thickness is ≤ 5 mm. When CT scans have slice thickness of >5 mm, the minimum size for a measurable lesion should be twice the slice thickness. MRI is also acceptable.

If prior to enrollment it is known that a patient is unable to undergo CT scans with intravenous (IV) contrast because of allergy or renal insufficiency, the decision as to whether a non-contrast CT or MRI (without IV contrast) will be used to evaluate the patient at baseline and during the study should be guided by the tumor type under investigation and the anatomic location of the disease. For patients who develop contraindications to contrast after baseline contrast CT is done, the decision as to whether non-contrast CT or MRI (enhanced or non-enhanced) will be performed should also be based on the tumor type and the anatomic location of the disease, and should be optimized to allow for comparison with the prior studies if possible. Each case should be discussed with the radiologist to determine if substitution of these other approaches is possible and, if not, the patient should be considered not evaluable from that point forward. Care must be taken in measurement of target lesions and interpretation of

non-target disease or new lesions on a different modality, since the same lesion may appear to have a different size using a new modality.

ENDOSCOPY, LAPAROSCOPY, ULTRASOUND, TUMOR MARKERS, CYTOLOGY, HISTOLOGY

Endoscopy, laparoscopy, ultrasound, tumor markers, cytology, and histology cannot be used for objective tumor evaluation .

ASSESSMENT OF TUMOR BURDEN

To assess objective response or future progression, it is necessary to estimate the overall tumor burden at baseline and use this as a comparator for subsequent measurements.

IDENTIFICATION OF TARGET AND NON-TARGET LESIONS

When more than one measurable lesion is present at baseline, all lesions up to a maximum of five lesions total (and a maximum of two lesions per organ) representative of all involved organs should be identified as target lesions and will be recorded and measured at baseline. This means that, for instances in which patients have only one or two organ sites involved, a maximum of two lesions (one site) and four lesions (two sites), respectively, will be recorded. Other lesions (albeit measurable) in those organs will be considered non-target lesions.

Target lesions should be selected on the basis of their size (lesions with the longest diameter) and should be representative of all involved organs, but in addition should lend themselves to reproducible repeated measurements. It may be the case that, on occasion, the largest lesion does not lend itself to reproducible measurement, in which circumstance the next largest lesion that can be measured reproducibly should be selected.

Lymph nodes merit special mention since they are normal anatomical structures that may be visible by imaging even if not involved by tumor. As noted above, pathological nodes that are defined as measurable and may be identified as target lesions must meet the criterion of a short axis of ≥ 15 mm by CT scan. Only the short axis of these nodes will contribute to the baseline sum. The short axis of the node is the diameter normally used by radiologists to judge if a node is involved by solid tumor. Lymph node size is normally reported as two dimensions in the plane in which the image is obtained (for CT, this is almost always the axial plane; for MRI, the plane of acquisition may be axial, sagittal, or coronal). The smaller of these measures is the short axis. For example, an abdominal node that is reported as being 20 mm \times 30 mm has a short axis of 20 mm and qualifies as a malignant, measurable node. In this example, 20 mm should be recorded as the node measurement. All other pathological nodes (those with short axis \geq 10 mm

Atezolizumab—F. Hoffmann-La Roche Ltd Page 177 of 214 Protocol GO41864, Version 2 but < 15 mm) should be considered non-target lesions. Nodes that have a short axis of <10 mm are considered non-pathological and should not be recorded or followed.

All lesions (or sites of disease) not selected as target lesions (measurable or non-measurable), including pathological lymph nodes, should be identified as non-target lesions and should also be recorded at baseline. Measurements are not required. It is possible to record multiple non-target lesions involving the same organ as a single item on the Case Report Form (CRF) (e.g., "multiple enlarged pelvic lymph nodes" or "multiple liver metastases").

CALCULATION OF SUM OF DIAMETERS

A sum of the diameters (longest diameter for non–lymph node lesions, short axis for lymph node lesions) will be calculated for all target lesions at baseline and at each subsequent tumor assessment as a measure of tumor burden.

Measuring Lymph Nodes

Lymph nodes identified as target lesions should always have the actual short axis measurement recorded (measured in the same anatomical plane as the baseline examination), even if the node regresses to < 10 mm during the study. Thus, when lymph nodes are included as target lesions, the sum of diameters may not be zero even if CR criteria are met, since a normal lymph node is defined as having a short axis of <10 mm.

Measuring Lesions That Become Too Small to Measure

During the study, all target lesions (lymph node and non–lymph node) recorded at baseline should have their actual measurements recorded at each subsequent evaluation, even when very small (e.g., 2 mm). However, sometimes lesions or lymph nodes that are recorded as target lesions at baseline become so faint on CT scan that the radiologist may not feel comfortable assigning an exact measurement and may report them as being too small to measure. When this occurs, it is important that a value be recorded on the CRF, as follows:

- If it is the opinion of the radiologist that the lesion has likely disappeared, the measurement should be recorded as 0 mm.
- If the lesion is believed to be present and is faintly seen but too small to measure, a default value of 5 mm should be assigned and "too small to measure" should be ticked. (Note: It is less likely that this rule will be used for lymph nodes since they usually have a definable size when normal and are frequently surrounded by fat such as in the retroperitoneum; however, if a lymph node is believed to be present and is faintly seen but too small to measure, a default value of 5 mm should be assigned in this circumstance as well and "too small to measure" should also be ticked).

To reiterate, however, if the radiologist is able to provide an actual measurement, that should be recorded, even if it is <5 mm, and in that case "too small to measure" should not be ticked.

Measuring Lesions That Split or Coalesce on Treatment

When non–lymph node lesions fragment, the longest diameters of the fragmented portions should be added together to calculate the sum of diameters. Similarly, as lesions coalesce, a plane between them may be maintained that would aid in obtaining maximal diameter measurements of each individual lesion. If the lesions have truly coalesced such that they are no longer separable, the vector of the longest diameter in this instance should be the maximum longest diameter for the coalesced lesion.

EVALUATION OF NON-TARGET LESIONS

Measurements are not required for non-target lesions, except that malignant lymph node non-target lesions should be monitored for reduction to <10 mm in short axis. Non-target lesions should be noted at baseline and should be identified as "present" or "absent" and (in rare cases) may be noted as "indicative of progression" at subsequent evaluations. In addition, if a lymph node lesion shrinks to a non-malignant size (short axis <10 mm), this should be captured on the CRF as part of the assessment of non-target lesions.

RESPONSE CRITERIA

CRITERIA FOR TARGET LESIONS

Definitions of the criteria used to determine objective tumor response for target lesions are provided below:

• Complete response (CR): Disappearance of all target lesions

Any pathological lymph nodes must have reduction in short axis to <10 mm.

- Partial response (PR): At least a 30% decrease in the sum of diameters of all target lesions, taking as reference the baseline sum of diameters, in the absence of CR
- Progressive disease (PD): At least a 20% increase in the sum of diameters of target lesions, taking as reference the smallest sum of diameters at prior timepoints (including baseline)

In addition to the relative increase of 20%, the sum of diameters must also demonstrate an absolute increase of \geq 5 mm.

 Stable disease (SD): Neither sufficient shrinkage to qualify for CR or PR nor sufficient increase to qualify for PD
CRITERIA FOR NON-TARGET LESIONS

Definitions of the criteria used to determine the tumor response for the group of nontarget lesions are provided below. While some non-target lesions may actually be measurable, they need not be measured and instead should be assessed only qualitatively at the timepoints specified in the schedule of activities.

CR: Disappearance of all non-target lesions and (if applicable) normalization of tumor marker level

All lymph nodes must be non-pathological in size (< 10 mm short axis).

- Non-CR/Non-PD: Persistence of one or more non-target lesions and/or (if applicable) maintenance of tumor marker level above the normal limits
- PD: Unequivocal progression of existing non-target lesions

SPECIAL NOTES ON ASSESSMENT OF PROGRESSION OF NON-TARGET LESIONS

Patients with Measurable and Non-Measurable Disease

For patients with both measurable and non-measurable disease to achieve unequivocal progression on the basis of the non-target lesions, there must be an overall level of substantial worsening in non-target lesions in a magnitude that, even in the presence of SD or PR in target lesions, the overall tumor burden has increased sufficiently to merit discontinuation of therapy. A modest increase in the size of one or more non-target lesions is usually not sufficient to qualify for unequivocal progression status. The designation of overall progression solely on the basis of change in non-target lesions in the face of SD or PR in target lesions will therefore be extremely rare.

NEW LESIONS

The appearance of new malignant lesions denotes disease progression; therefore, some comments on detection of new lesions are important. There are no specific criteria for the identification of new radiographic lesions; however, the finding of a new lesion should be unequivocal, that is, not attributable to differences in scanning technique, change in imaging modality, or findings thought to represent something other than tumor (for example, some "new" bone lesions may be simply healing or flare of preexisting lesions). This is particularly important when the patient's baseline lesions show PR or CR. For example, necrosis of a liver lesion may be reported on a CT scan report as a "new" cystic lesion, which it is not.

A lesion identified during the study in an anatomical location that was not scanned at baseline is considered a new lesion and will indicate disease progression.

If a new lesion is equivocal, for example because of its small size, continued therapy and follow-up evaluation will clarify if it represents truly new disease. If repeat scans confirm

Atezolizumab—F. Hoffmann-La Roche Ltd Page 180 of 214 Protocol GO41864, Version 2 there is definitely a new lesion, progression should be declared using the date of the initial scan.

CRITERIA FOR OVERALL RESPONSE AT A SINGLE TIMEPOINT

 Table 1 provides a summary of the overall response status calculation at each response assessment timepoint for patients who have measurable disease at baseline.

Table 1Criteria for Overall Response at a Single Timepoint: Patients
with Target Lesions (with or without Non-Target Lesions)

Target Lesions	Non-Target Lesions	New Lesions	Overall Response
CR	CR	No	CR
CR	Non-CR/non-PD	No	PR
CR	Not all evaluated	No	PR
PR	Non-PD or not all evaluated	No	PR
SD	Non-PD or not all evaluated	No	SD
Not all evaluated	Non-PD	No	NE
PD	Any	Yes or no	PD
Any	PD	Yes or no	PD
Any	Any	Yes	PD

CR = complete response; NE = not evaluable; PD = progressive disease; PR = partial response; SD = stable disease.

Table 2Criteria for Overall Response at a Single Timepoint: Patients
with Non-Target Lesions Only

Non-Target Lesions	New Lesions	Overall Response
CR	No	CR
Non-CR/non-PD	No	Non-CR/non-PD ^a
Not all evaluated	No	NE
Unequivocal PD	Yes or no	PD
Any	Yes	PD

CR=complete response; NE=not evaluable; PD=progressive disease.

^a "Non-CR/non-PD" is preferred over "stable disease" for non-target disease since stable disease is increasingly used as an endpoint for assessment of efficacy in some trials; thus, assigning "stable disease" when no lesions can be measured is not advised.

MISSING ASSESSMENTS AND NOT EVALUABLE DESIGNATION

When no imaging/measurement is done at all at a particular timepoint, the patient is not evaluable at that timepoint. If measurements are made on only a subset of target lesions at a timepoint, usually the case is also considered not evaluable at that timepoint, unless a convincing argument can be made that the contribution of the individual missing lesions would not change the assigned timepoint response. This would be most likely to happen in the case of PD. For example, if a patient had a baseline sum of 50 mm with three measured lesions and during the study only two lesions were assessed, but those gave a sum of 80 mm, the patient will have achieved PD status, regardless of the contribution of the missing lesion.

